**d. Early stopping rules.**

At any point in the study, the subject may decline to participate. Indications for stopping are the development of severe adverse events. The IRB will be informed of any adverse events. Any serious adverse events will result in study discontinuation.

If propranolol has not yet been administered, and systolic BP  $<90$  or HR  $<50$  the study will continue without giving propranolol. The P.I. should be notified of this occurrence. If propranolol has been administered, and systolic BP  $<90$  or HR  $<50$  the study will be stopped early. The subject will be awoken from sleep to assess symptoms, hemodynamics, and orthostasis. The P.I. is to be notified for severe nocturnal hypoxemia with SpO2 consistently  $<85\%$  for  $>5$  min, or unstable cardiac arrhythmia on EKG during sleep.

**8. Risks**

- a. Medical risks, listing all procedures, their major and minor risks and expected frequency.
- **Withdrawal of CPAP:** During abstinence from CPAP over 3 days, subjects may experience relatively unrefreshing sleep. During the night, they may experience arousals from sleep, morning headache. During the daytime, they may experience subjective and/or objective daytime sleepiness. The risk of sleepiness contributing to an accident such as work-related injury or motor vehicle collision is also increased. Chronically, OSA is associated with increased risks of hypertension, diabetes, stroke, and ischemic heart disease. In a recent study on the effects of 2-weeks of CPAP withdrawal, there were modest and gradual increases in daytime blood pressure and heart rate [35, 36]. Risks of stopping CPAP up to 2 weeks is therefore a low-risk, high yield research method. In this study, withholding CPAP for a few days is associated with even fewer risks.
- **Propranolol:** The main risk of propranolol is an overdose leading to bradycardia and hypotension, but not this is not anticipated at this low clinical starting dose. Common side effects are dizziness, fatigue, constipation. In the aforementioned BHAT trial [45] in which 1,915 persons received propranolol and 1,921 placebo, the following adverse effects occurred that were statistically significant between propranolol and placebo ( $p < 0.05$ ) resulting in study medical withdrawal: hypotension (1.2% versus 0.3%); reduced sexual activity (2% vs. 0%). In terms of patient complaints, those effects that were statistically significant ( $p < 0.05$ ) between propranolol and placebo were: bronchospasm (31% vs. 27%), cold hands or feet (10% vs. 7.7%), tiredness (66.8% vs. 62.1%), diarrhea (5.5% vs. 3.8%). Notably this was a 25-month study and our study only administers a single dose of drug. Serious but rare hypersensitivity reactions have been reported including anaphylaxis and cutaneous reactions such as Stevens-Johnson syndrome, toxic epidermal necrolysis, dry eyes, exfoliative dermatitis, erythema

multiforme, urticaria, alopecia, SLE-like reactions, and psoriaform rashes[41]. Beta blockers, as a class, can cause bronchospasm in those with significant underlying asthma.

- Isotope infusion and ingestion: Stable isotopes are naturally occurring, non-radioactive compounds normally present in the body at low levels. Infusion or ingestion of isotopes at very low tracer doses transiently increases the level of these molecules by <10% and is not associated with any adverse effects. As is the case with any infusion, there is a small chance of infection.
- DEXA scan: DEXA scans are considered safe and deliver minimal radiation.
- Venipuncture: May be associated with discomfort and bruising.

Phlebotomy: In total, the blood collected will be approximately 116 cc (as compared to approximately 350 mL during a donation). Theoretically, if too much blood is lost, this could lead to low blood pressure and cardiovascular stress or dizziness.

- Nasal dilator strips: These are non-latex, adhesive tape applied to the nose designed to mitigate snoring and nasal congestion. There may be discomfort using NDS and they are likely to be inferior to CPAP for treating OSA.
- Confidentiality of genetic material: There is the risk that genetic data is revealed outside the study. Information can also lead to unwanted psychological or financial consequences if it were released to a third party.

b. Steps taken to minimize the risks.

- Withdrawal of CPAP: The period of withdrawal is kept relatively short, at 3 nights. Subjects will be advised to arrange transportation home so that they do not need to drive. They will be advised to increase their total sleep time, if necessary, during CPAP abstinence to minimize sleep deprivation off CPAP. On the day of the non-CPAP sleep study, if they plan to drive home themselves, they will be provided with an additional 3-4 hours of time in the lab to sleep before discharge. Patients at increased cardiovascular risk (uncontrolled hypertension, heart failure) are excluded. Participants with high-risk occupations requiring vigilance, such as commercial drivers and pilots, will be excluded. Participants who have ever been in a near-miss or motor vehicle accident due to sleepiness will be excluded. When communicating with patients about their off-CPAP visits, patients will be asked in the 1-2 days before their visit if they have experienced any near-miss events or motor vehicle accidents. If they have, then they will be excluded from the study, advised to resume CPAP immediately, and to avoid driving or other high risk activities until they have used CPAP for 3 nights.
- Propranolol: Risks are minimized by providing only a single dose of drug at a low clinical dose. We will exclude patients with contraindications to the drug or those who are taking medications that affect (or are affected by) propranolol metabolism. We will exclude elderly (>65 years old) in whom propranolol LA has not been well studied. We will monitor blood pressure and heart rate during the study. We perform a screening EKG to exclude those with underlying conduction or rhythm disorders. The EKG will be reviewed by [name], [name], or [name]. All physicians are board certified in pulmonary and critical care medicine. If a conduction or rhythm abnormality is detected (see exclusion criteria) the participant will be informed of the finding. With the participant's consent, we will also provide a copy of the EKG to the patient, the patient's primary care provider or cardiologist, and provide them with contact information for the Johns Hopkins cardiology clinic for further evaluation. Any unstable arrhythmia such as sustained wide complex tachycardia, atrial fibrillation with rapid ventricular response, or complete heart block will be dealt with as a medical emergency with transfer to the emergency room. In terms of bronchospasm, patients with a history of asthma (no worse than mild intermittent as per NHLBI 2007 guidelines) including those on regular controller medications will be excluded.

- Isotope infusion and ingestion: To mitigate any chance of infection from infused isotopes, they will be compounded in a sterile facility by a registered pharmacist. The infusion is also filtered through a 22 micron (Millipore) filter during infusion. The patient will be monitored for any infection or allergic reaction to the infusion, and the infusion stopped in the event of the development of symptoms such as urticaria, flushing, nausea, fever chills.
- Venipuncture: Discomfort, bruise formation, and infection will be minimized by use of sterile supplies and aseptic technique by trained personnel.
- Phlebotomy: The volume of each blood draw is minimized to balance safety with the need to obtain a useful amount of plasma after centrifugation. The risk of inducing hemodynamic or cardiovascular stress is minimized by excluding those with significant baseline anemia (hemoglobin <10 mg/dl). Those found to have anemia will be informed of the results and advised to seek medical evaluation as appropriate.
- DEXA scan: DEXA uses a beam of very low radiation, delivering <10% radiation as during a clinical chest X-ray. Each participant will only require 1 DEXA scan.
- NDS: This is only being used for a few nights as a CPAP placebo.
- Confidentiality of genetic material: Blood is de-identified using the study IDs. When DNA is purified, a second number will be assigned to the DNA material. We will maintain a separate “key” linking this DNA sample to the study ID. This “key” will be stored on an encrypted server, and access to this server will be limited to only certain members of the study team. Participants may opt out from the genetic analysis.

c. Plan for reporting unanticipated problems or study deviations.

The plan for collection, description, monitoring and analysis of adverse events is presented in accordance with guidelines for adverse event reporting to the IRB. We will use the following definitions and grading scales for monitoring purposes:

Definition of adverse event (AE): any unfavorable and unintended sign (including an abnormal laboratory finding), symptom or disease temporarily associated with the use of a medical treatment or procedure regardless of whether it is considered related to the medical treatment or procedure

Definition of serious adverse event (SAE): any event that is fatal or life-threatening, that is permanently disabling, requires or extends hospitalization of the subject, represents a significant overdose or breach of protocol, suggests that a drug, device, or procedure used in a research protocol has produced a congenital anomaly or cancer, or in the opinion of the investigator, represents other significant hazards or potentially serious harm to the research subject or others

Adverse events will be graded as (a) mild (adverse event of little clinical significance), (b) moderate (adverse event between mild and severe – causing some limitation of usual activities), or (c) severe (an event that results in death, is life-threatening, requires or prolongs hospitalization, causes persistent or significant disability/incapacity, represents a significant overdose or breach of protocol, results in congenital anomalies/birth defects or produces cancer, or in the opinion of the investigator, represents other significant hazards or potentially serious harm to the research subject or others), and their attribution will be classified as (a) not related (clearly not related), (b) possible (may be related), (c) probable (likely related), (d) definite (clearly related) or (e) unable to assess.

Study participants will be monitored throughout the study for adverse events, both anticipated and unexpected. The Principal Investigator will serve as the monitor. Adverse events will be reviewed by the Principal Investigator, managed according to standard clinical practice, and classified for severity and

attribution. Serious adverse events or unexpected adverse events will be recorded on the appropriate IRB form and reported to the IRB and RSA as required. All adverse events will be tracked to resolution.

The principal investigator will provide an interim report of all adverse events to the IRB at the time of continuing review. In addition, the Principal Investigator will provide the RSA a tabulation of the number of subjects enrolled, number of specific adverse events and a summary of the study at regular intervals. The RSA in collaboration will monitor the frequency of adverse events and serious adverse events

d. Legal risks such as the risks that would be associated with breach of confidentiality.

Breach of confidentiality would result in unauthorized individuals having access to information about the participant's medical history. To prevent unauthorized access, (1) all files related to study subjects will be locked in file cabinets; (2) digital files will be restricted to study investigators and associated staff, on a need-to-know basis. (3) Subject data will be stored with unique identifiers and will be password protected. Encryption algorithms that can only be reversed with password access will be implemented. All computers will require log on passwords.

e. Financial risks to the participants.

Study-related assessments will not be charged to the subject. Parking fees will be paid. Subjects will be responsible for any treatment of conditions that are uncovered as part of the study evaluations or if they are injured as a result of being in the study.

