**Study overview:** There are a total of 4 study visits. The first visit is a consent, screening, and randomization visit. After consent, a screening EKG will be performed to exclude rhythm or conduction abnormalities and a urine pregnancy test to exclude pregnancy in potentially pregnant females. (If the participant has had a clinical EKG or EKG report in the last year that does not indicate any conduction disorders listed in the exclusion criteria, the screening EKG may be deferred.) A point of care screening test for hemoglobin will also be performed to exclude pre-existing anemia. Patients with a hemoglobin < 10 g/dL are ineligible for this study. They will be provided with ClearPassage® NDS to use at home during CPAP withdrawal nights.

Thereafter, there are 3 overnight visits to the CRU in random order. This protocol compares nocturnal metabolism in treated OSA (CPAP), untreated OSA (NDS), and beta-blocked OSA (NDS) in the same subject. OSA nights are performed in the lab after using NDS instead of CPAP for 2 nights at home.

**Covid-19 screening:** We will screen participants before their arrival for their each sleep study with a Covid-19 test. A negative screen within 72 hours of the CPAP visit will be needed prior to admission for the CPAP study visit.

During each OSA visit, propranolol or placebo is taken in the evening, in random order. Frequent blood sampling is performed throughout the visit. In the morning, DEXA (only 1 DEXA needed for entire study) is performed. We are targeting 1 week between visits, but will allow flexibility in scheduling patients unable to schedule 3 consecutive visits exactly 1 week apart; in this scenario we will allow a duration of  $\geq$  4 days or  $\leq$  3 weeks between visits. Each visit we will also administer stable isotopes to measure detailed lipid metabolism.

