**Each sleep study night will consist of the following procedures:**

*Pre-sleep procedures.* Subjects will undergo a history and physical examination. They will report to the CRU at 4:00 PM and undergo anthropometric assessment including weight, height, neck, and waist circumference. At 5:30 PM, they will eat a standard dinner containing 30% fat, 50% carbohydrate, and 20% protein with kcal based upon the Mifflin-St Jeor formula. Two peripheral IVs (18 to 20 gauge) will be placed. All samples are obtained through the IV without disturbing the subject during sleep. Blood pressure will be checked at 6:30 PM, before administration of study drug. If systolic blood pressure is <90 or the heart rate is <50 then no drug will be administered. (In the event that this occurs, the study will still proceed so that CPAP and OSA nights can be compared and analyzed as a "no drug" group.) If blood pressure and heart rate are acceptable, propranolol LA 80 mg, or placebo (random order, crossover on study night 2 and 3) will be given. Participants and the investigators will be blinded to drug assignment.

*PSG setup.* On each study night from 10:30 PM until 6:30 AM, a PSG will be performed. The sleep study will include electroencephalography, electrooculography, oxygenation, respiratory effort, CPAP airflow, and transcutaneous CO2 monitoring. Respiratory effort will be measured by thoraco-abdominal movement assessed by mercury strain gauges. Surface electrodes will be placed at C3A2 and C3O1, a submental electrode, and left and right electro-oculogram will be used to stage sleep. Electrocardiograph (EKG) tracings will be recorded from three chest electrodes. Continuous measurement of oxygen saturation will be recorded using an ear oximeter (model No 472-1A, Hewlett Packard, Waltham, Mass). Transcutaneous CO2 will be monitored using a Radiometer TCM-4 device. Signals from the electroencephalograph, EKG, electromyogram, electrooculogram, respiratory strain gauge, ear oximeter and thermistors will be recorded on a computer with RemLogic software.

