**Stable isotope ingestion and infusions.** Stable isotopes are being used in this project to quantify rates of adipose tissue lipolysis (infusions of [ $^{13}\text{C}_3$ ]glycerol and [ $^{13}\text{C}_{16}$ ]palmitate) and rates of fatty acid oxidation (FAO, ingestion of [ $^2\text{H}_{31}$ ]palmitate). Ingested  $^2\text{H}$  molecules on palmitate are incorporated into plasma  $^2\text{H}_2\text{O}$  during FAO and detected by mass spectrometry. This technique permits FAO measurement without needing to capture exhaled  $\text{CO}_2$ , measure  $\text{VCO}_2$ , or administer acetate to adjust for  $\text{CO}_2$  sequestration. By adopting this approach, FAO can be assessed without interrupting sleep, respiratory monitoring, or CPAP. **Catheters:** Before dinner, an IV will be inserted into a vein of each arm; one for blood sampling, and the other for infusion of labeled glycerol and palmitate. Patency of all catheters will be maintained by saline infusion. **Infusions of tracers:** On each visit, after obtaining a blood sample to determine background enrichment, a constant infusion of [ $^{13}\text{C}_3$ ]glycerol ( $0.1 \mu\text{mol}\cdot\text{kg}^{-1}\cdot\text{min}^{-1}$ ; Sigma-Aldrich, St. Louis, MO) will be administered. Glycerol and palmitate stable isotopes are obtained as a sterile powder from Sigma-Aldrich, and compounded and dispensed by the Johns Hopkins research pharmacy. The product is initially tested for sterility and pyrogenicity by Sigma-Aldrich. In the Johns Hopkins research pharmacy, the powders will be solubilized and aliquots tested for sterility and pyrogenicity. Infusions are given at a “tracer” dose detectable only by gas chromatography/mass spectroscopy (GC/MS). All tracers in this protocol are tested for microbiological contamination, and are exempt from FDA IND status (see correspondence with FDA # PIND 132066).

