In total, the blood collected will be approximately 30 samples x 4 mL = 120 mL. For patients that consent to isolation of genetic material, the total will be 136 cc. This quantity is less than half the volume of blood given during a donation (350 mL). A morning urine sample will be collected for measurement of catecholamines. The final blood sample will be drawn at 9 AM, after which the IV will be removed, and the subject will be discharged from the CRU. Samples will be frozen at -80°C for research pertaining to metabolic effects of OSA, with the consent of participants.

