**Definition of treatment failure or participant removal criteria.**

Participants will be removed from the study if they do not meet eligibility criteria. Otherwise, this study is expected to induce OSA and its consequences, and the drug is being used as a tool to test mechanisms rather than treat a specific disorder. Patients may be removed from the study if they elect to withdrawal at any time.

**f. Description of what happens to participants receiving therapy when study ends or if a participant's participation in the study ends prematurely.**

Propranolol is given only one time per participant and is not considered therapy, but a mechanistic intervention. After each study visit, CPAP is resumed. Sleep study results will be discussed with the patient upon completion of the study. When clinically appropriate, referral for treatment will be provided. Patients may request results of their sleep study before completion of the study.

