**Exclusion Criteria:**

1. Cardiovascular risks
  - a. Decompensated congestive heart failure
  - b. Atrial fibrillation, sick sinus syndrome, 2nd or 3rd degree heart block, pacemaker implantation, Wolff-Parkinson-White Syndrome (if not known, will check on a screening EKG)
  - c. Uncontrolled hypertension  $> 170/110$
  - d. History of postural hypotension.
  - e. Resting systolic pressure  $<90$  or heart rate  $< 50$  on screening visit
2. Drug interactions – currently taking any of the following drugs Subjects on these medications are excluded from participation and will not have the drug in question discontinued for the purposes of participation in the study.
  - a. Calcium channel blockers that reduce heart rate (diltiazem, verapamil, fendiline, gallopamil)
  - b. Sympatholytic drugs: any other beta blocker; clonidine, terazosin or doxazosin; reserpine
  - c. Anti-arrhythmic drugs: (e.g. amiodarone, sotalol, digoxin, quinidine, lidocaine, propafenone)
  - d. Coumadin (propranolol may prolong INR)
  - e. Drugs that Inhibit CYP2D6, CYP1A2, or CYP2C19: amiodarone, ciprofloxacin, cimetidine, delavudin, fluconazole, fluoxetine, fluvoxamine, imipramine, isoniazid, paroxetine, quinidine, ritonavir, rizatriptan, tenioposide, theophylline, tolbutamide, zileuton, zolmitriptan
  - f. Drugs that increase hepatic metabolism of propranolol: rifampin, ethanol, phenytoin, and phenobarbital
  - g. Neuroleptics/anxiolytics: (thioridazine, chlorpromazine – may increase propranolol level), haloperidol, valium
  - h. Illicit drugs such as cocaine or amphetamines.

3. Other medical conditions
  - a. Sleep disorder other than OSA, including: restless leg syndrome, parasomnia, or narcolepsy.
  - b. Shift work or circadian rhythm disorder that is expected to prevent good sleep as scheduled in the protocol
  - c. Insulin-dependent diabetes mellitus
  - d. Myasthenia gravis
  - e. Pheochromocytoma
  - f. Uncontrolled bronchospastic lung disease such as COPD, mild persistent or worse asthma, as well as those requiring maintenance therapy.
  - g. Current smoking
  - h. Chronic renal or liver failure
  - i. Known pregnancy, by urine testing in women of child-bearing age; nursing mothers
  - j. Known hypersensitivity to any beta blocker
  - k. Hemoglobin < 10 g/dL on point of care screening

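### The Risks section gives one night's blood volume (about 116 mL) as the study total; three nights take about 350 to 360 mL, and no cumulative figure is stated

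*Protocol*

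**What the plan says.** Section 8a of the protocol, under Phlebotomy, states: "In total, the blood collected will be approximately 116 cc (as compared to approximately 350 mL during a donation"). It adds that losing too much blood could in theory cause low blood pressure, cardiovascular stress or dizziness. Nothing there limits the figure to one visit.

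Section 4 gives a similar figure under the procedures for each sleep study night: "In total, the blood collected will be approximately 30 samples x 4 mL = 120 mL". It raises this to 136 cc for participants who consent to genetic sampling and says the amount is under half of a 350 mL donation. The study overview in section 4 specifies three overnight visits.

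Section 8b gives two phlebotomy measures. One is to keep each draw small. The other is an entry exclusion: "The risk of inducing hemodynamic or cardiovascular stress is minimized by excluding those with significant baseline anemia (hemoglobin <10 mg/dl"). The study overview places the test at the first visit: "A point of care screening test for hemoglobin will also be performed to exclude pre-existing anemia". Exclusion criterion 3k reads "Hemoglobin < 10 g/dL on point of care screening". No later hemoglobin test is described.

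**The concern.** The Risks section is where an ethics board looks for the exposure. Read as written, the whole study takes about a third of a donation. If the figure covers one of three nights, the stated exposure is about a third of the true one, and the reassurance drawn from the donation comparison does not carry over to the study.

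The hemoglobin limit is linked to this. It is the only measure directed at blood sampling that depends on the individual participant, and it is applied before the first of three nights. The sampling itself lowers hemoglobin, so someone admitted just above the limit may start a later night below it without anyone knowing. The stake is an accurate risk statement and a modest safety margin, not the validity of any result.

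**Working it through.** **Reproducing 116 mL.** Inputs from section 4 (PSG setup; Blood sampling): first sample 5:30 PM, hourly while awake, every 30 minutes from 10:30 PM to 6:30 AM, last sample 9:00 AM, 4 mL each, with extra samples near the end of each of four palmitate infusions.

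- Evening, 5:30 to 9:30 PM hourly: 5
- Sleep period, 10:30 PM to 6:30 AM every 30 minutes: 17
- Morning, 7:30, 8:30 and 9:00 AM: 3
- Subtotal: 25 samples × 4 mL = 100 mL
- One extra per infusion (assumed; the number is not stated): 25 + 4 = 29, and 29 × 4 = **116 mL**
- Two extra per infusion: 33 × 4 = 132 mL

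The protocol's rounded count gives 30 × 4 = 120 mL, and 120 + 16 = 136 mL with genetic sampling. So 116 mL is a one-night figure. Spread over three nights it would allow 116 / (3 × 4) = 9.7 samples a night, while the sleep period alone needs 17.

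**Study totals against the 350 mL comparator.**

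| Per night | % of 350 | Three nights | % of 350 | With one full repeat night |
|---|---|---|---|---|
| 116 mL | 33% | 348 mL | 99% | 464 mL |
| 120 mL | 34% | 360 mL | 103% | 480 mL |
| 136 mL | 39% | 408 mL | 117% | 544 mL |

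The last row assumes the genetic sample is taken every night; taken once, the three-night total is 360 + 16 = 376 mL. Repeat nights are allowed under Post-test procedures in section 4. The protocol puts participation at about 2 to 6 weeks. At the minimum spacing of 4 days, the first and third nights are 8 days apart.

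**What this could do to hemoglobin (illustration only).** The documents give no blood volumes or hemoglobin distribution. Assume blood volume B of 4 to 7 L, lost volume replaced (section 4 notes "Patency of all catheters will be maintained by saline infusion"), and no red-cell recovery between visits. After drawing V mL, hemoglobin = starting value × exp(−V/B).

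- Start of visit 3, V = 240, from 10.0 g/dL: 10 × exp(−240/4000) = 9.42, to 10 × exp(−240/7000) = 9.66.
- If half the loss has been recovered, net V = 120: 9.70 to 9.83.
- Screening value needed to start visit 3 at 10 or above: 10 × exp(240/B) = 10.35 to 10.62. With genetic sampling at both earlier visits, V = 272: 10.40 to 10.70.
- Needed to start a repeat night after three visits, V = 360: 10.53 to 10.94. With genetic sampling each time, V = 408: 10.60 to 11.07.

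A re-check trigger of about 11 g/dL therefore covers nearly all of these cases.

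**The case against.** Several points on the other side are sound.

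- **The 10 g/dL limit is an entry criterion.** The study overview, criterion 3k and section 8b all tie it to screening or baseline. A reader might infer that someone below 10 at visit 3 has breached eligibility, especially as the protocol says "Participants will be removed from the study if they do not meet eligibility criteria". The text does not support that: the general removal sentence does not turn a screening criterion into a continuing one. Nor does any passage say that a value in the mid-9s is unsafe for another 120 mL taken in 4 mL samples.
- **The 6:30 PM check is not an eligibility re-check.** The rule "If systolic blood pressure is <90 or the heart rate is <50 then no drug will be administered" governs dosing, so it does not show that hemoglobin was left out of a nightly repeat of the entry criteria. It also does not stop sampling, because the night goes ahead without drug.
- **Other protections bear on the named harms.** These are a history and physical each night, blood pressure several times per visit, EKG recording, exclusion for postural hypotension and low resting pressure, and the early stop after propranolol (section 7d). Hemoglobin is the only participant-level measure directed at blood sampling, not the only protection.
- **One night against one donation is a fair comparison for acute loss**, and a careful reader can multiply by three.

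The last point does not rescue the Risks wording, which claims a total and gives no per-visit label. The first three mean that the missing re-test is a reasonable improvement to suggest rather than a breach of the protocol's own rule.

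**Conclusion.** The volume statement is wrong as written. The figure given for the study covers one night. The total is about 348 to 360 mL, up to about 408 mL with genetic sampling every night, plus about 120 mL (136 mL with genetic sampling) for any repeat night. This rests only on the protocol's per-night schedule and three visits and needs no physiological assumption.

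The hemoglobin part is weaker. It is a fact that the test is done once, before sampling. The possible shortfall at visit 3 is about 0.2 to 0.6 g/dL for someone screened at exactly 10.0, and that depends on assumed blood volume and recovery. The number of participants near the limit is unknown and probably small.

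Three stronger conclusions might be drawn, and the documents do not support them: that the sampling is unsafe, that participants were misinformed (the consent pages were removed and cannot be checked), or that everyone needs re-testing or a higher entry limit. The last is a trade-off, not a demonstrated need. No endpoint, sample size or analysis is affected.

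**What to change.** 1. **Section 8a, Phlebotomy.** State approximately 120 mL per visit (136 mL with genetic consent) and about 360 mL over three visits (up to about 408 mL). Say that this is about the volume of one donation, spread over about 2 to 6 weeks, and that a repeat night adds about 120 mL (136 mL with genetic sampling).
2. **Section 4, Blood sampling.** Limit the comparison with under half a donation to a single visit.
3. **Section 8b.** Correct the hemoglobin unit from mg/dl to g/dL, as in section 4 and criterion 3k. This is clerical.
4. **Suggested addition.** For participants who screened close to the limit (for example below 11 g/dL), repeat the point-of-care hemoglobin test before visits 2 and 3 and before any repeat night, using blood already drawn at the 5:30 PM sample. That sample precedes dinner, tracers and study drug. A low value would postpone the visit within the allowed 3-week spacing before any withdrawal is considered.

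Items 1 to 3 cost only the edit. Item 4 costs a few point-of-care tests and an occasional delayed visit. On a nasal-strip night, a delay also means repeating the two home nights off CPAP. In the worst case a drug-placebo pair is lost, which matters a little against the 16 participants that the SAP's sample size requires. Restricting the re-test to those near the limit keeps that cost small.
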